## Neuromechanical assessments of walking

Neuromechanical assessments, such as the analysis of muscle activation and movement during walking, will be conducted during testing for both Aim 1 and 2. During Aim 1, the assessments will occur before and after the completion of up to 30 minutes of treadmill walking. As most participants will not tolerate 30 minutes of uninterrupted walking, the session will be divided with rest breaks as needed to deliver a total of ~30 minutes of walking. tsDCS at one of the two dosages will be applied for up to 30 minutes. The goal of the protocol is to complete 30 minutes of walking with stimulation. However, we recognize that this protocol may need to be adjusted slightly for some individuals based on aspects such as comfort or fatigue. During Aim 2, neuromechanical assessments of walking will be conducted before and after the 16 sessions of locomotor training. To perform these neuromechanical assessments, participants may be asked to perform activities such as treadmill walking or overground walking at self-selected or fastest-comfortable walking speeds, walking backward, and stepping over an obstacle. Participants may use any typically used orthotics (i.e. AFOs) or gait assistive devices required by the participant.

All testing procedures will be closely monitored by a physical therapist who will monitor the participant's vital signs for safety and provide rest breaks as needed or requested. A safety harness attached to an overhead support system may be used when performing walking overground. Testing will also occur while walking on a treadmill using a harness to secure the participant to an overhead support system to provide partial body weight support if needed. Participants may opt not to perform any walking task, and all tasks will be adjusted for each participant's functional level. Study procedures will be explained ahead of time and participants will be asked to wear appropriate clothing for participation. Participants will be able to sit comfortably during the set-up procedures. During the set-

[figure not shown]
up, small reflective markers and EMG sensors will be affixed to the skin and will be removed at the conclusion of the assessment (details below).

The following procedures will be completed during the neuromechanical assessments:

- Measurement of joint motions during standing and walking- To quantify trunk and lower extremity joint motions, a 12-camera three-dimensional motion analysis system will be used to collect marker data and measure joint kinematics during walking tasks. Small, lightweight reflective markers will be placed on the upper and lower extremities and the trunk using an established marker set. To reduce artifact and improve accuracy of motion analysis data, reflective markers will be placed directly on the skin when possible using hypoallergenic double-sided tape. Individuals will be asked to wear tight, minimal clothing, such as tank tops and athletic shorts, to provide access to bony, anatomical landmarks as able.
- Recording of muscle activation- A wireless, 16-channel surface electromyography (EMG) system will be used to record muscle activation during the standing and walking activities. In the small area over the muscle where the sensors will be placed, the skin will be shaved and cleaned with alcohol prior to attaching the sensors with hypoallergenic double-sided tape. These procedures optimize EMG signals by reducing noise and impedance. EMG signals will be recorded using the motion capture software to synchronize collection of the EMGs and motion data (kinematics).
- Assessment of kinetics and spatio-temporal movement characteristics-Ground reaction forces (kinetics) will be recorded during the walking activities. The participants will be asked to walk over the standard built-in force plates, which are flush with the floor and are not an obstacle or tripping hazard. This will be done while they also are wearing the EMGs and reflective markers so that all data are captured simultaneously. During the session, the participant may be asked to stand or walk over a 12' instrumented walkway (i.e. GaitRite). The walkway appears like a flat, carpeted surface and has embedded sensors to record foot falls and foot placement. The edges of the walkway will be taped down to be nearly flush with the floor and to minimize the possibility of tripping. Participants will be guarded at all times and/or an overhead harness may be

used. The instrumented walkway will provide quantitative data regarding the spatial and temporal characteristics of standing and walking.

Recording of cortical activity- Functional near infrared spectroscopy (fNIRS) will be used to assess brain/neural activity required for the individual to perform the standing and walking tasks assessed during the motion capture biomechanical testing. fNIRS uses non-invasive sensors that are light-emitting diodes to illuminate oxygenated hemoglobin in superficial brain tissue. This approach is used to indirectly quantify neural activity. The sensors are attached

to a lightweight strap which will be placed around the participant's forehead to monitor neural activity in the pre-frontal cortex. No skin preparation is required. The data are transmitted wirelessly to a computer to record the data and for future analysis. This information can be used to better understand the cognitive and attentional efforts used while performing the walking tasks, which may relate to safety and fall risk.

# Reflex testing

To quantify stimulation induced effects on spinal activation, H-reflex assessment of the soleus muscle will be conducted according to accepted and widely used methodology. 64,65 First, the H-reflex will be recorded while the participant rests in a semi-reclined positioned with the foot supported in slight ankle dorsiflexion (~10 degrees) and the knee in 30 degrees of flexion. Stimulation will be delivered via a cathode placed in the popliteal fossa and an anode placed above the patella. EMGs will be recorded from the soleus with bipolar surface electrodes placed 3 cm apart. M-waves and H-waves will be recorded over a range of intensities to acquire a full recruitment curve, starting at subthreshold intensities and increasing until the reflex amplitude reaches a plateau. The range of intensities is necessary so that a response equivalent to 50% of Hmax can be elicited for use in analyses comparing between individuals. Second, modulation of the H-reflex may be examined during walking. The cathode and anode will be secured with adhesive tape or a self-adhering wrap (e.g., Coband) with care being taken to avoid restricting movement of the knee. Mmax will be re-established in the standing position for analysis of walking H-waves. During walking, stimulation intensity will be adjusted every stimulation to maintain a consistent M-wave amplitude relative to the maximum M-wave (M-max). We will visually determine events of the gait cycle to manually trigger every two to five seconds and collect H-waves during both mid-stance and mid-swing.

The electrical stimulation for H-reflex testing may be uncomfortable at times, but it is not dangerous. The discomfort is temporary and lasts only a few seconds. Evidence of stimulation induced effects on spinal excitability will provide insight into the potential underlying mechanisms mediating changes in muscle activation and limb control during tsDCS and walking.

#### Clinical assessments

Clinical assessments will be used to characterize the participants during Aim 1 and to examine changes following the regimen of locomotor training in Aim 2. These assessments will include:

[figure not shown]
- Spinal Cord Assessment Tool for Spastic Reflexes (SCATS)- The SCATS is a reliable and valid tool for assessing spasm activity of flexor and extensor muscle groups as well as spastic hypertonia in patients with spinal cord injury.
- 10-Meter Walk Test (10MWT)- This validated measures assesses forward walking speed.
- 6-Minute Walk Test (6MWT)- The 6MWT is a reliable and valid tool for assessing walking endurance.

- International Standards for the Neurologic Classification of Spinal Cord Injury (ISNCSCI)- Clinical tests of sensory and motor function to classify level and severity of spinal cord injury (ASIA impairment scale)
- 30-second Chair Stand Test (30-s CST)- Performance assessment to measure functional lower limb muscle strength used to move from sitting to/from standing
- Activities Specific Balance Confidence (ABC) Scale- Questionnaire to assess self-reported balance confidence in varied functional situations such as walking in a parking lot or in the home
- Neuromuscular Recovery Scale (NMRS)- Performance assessment of functional motor recovery such as sitting and standing function
- 3-meter Backward Walk Test- An assessment of backward walking speed
- Postural muscle strength assessment Seated clinical test of postural muscle strength using hand-held force dynamometry

## Delivery of tsDCS

tsDCS will be delivered to the low back, over the lumbar region of the spinal cord, using a commercially available direct current stimulation unit (Soterix Medical Inc). Each tsDCS electrode is comprised of a carbon rubber electrode encased in a saline-soaked sponge. The electrodes will be placed on the participant using a previously established configuration to target the lumbosacral cord with two electrodes on the abdomen placed

to the left and right of the umbilicus and one over the lumbar spinal cord at the level of the 11th and 12th thoracic vertebrae. A large elastic bandage with Velcro closure will be wrapped around the abdomen to hold the electrodes firmly in place. Participants will be closely monitored for any adverse responses such as skin irritation and pain. This electrode configuration has been shown to appropriately target the lumbosacral spinal cord, as validated

by modeling of electrical current flow and by gains in lower extremity motor performance. A low dosage of ≤ 2.5 mA stimulus will be used for the "higher" dosage. This dosage (or very similar) has been used in numerous prior studies and has been shown to be well-tolerated and to produce measurable changes in reflex activity and/or lower extremity motor performance. An identical montage and stimulation arrangement will be used for the "lower" dosage, except the stimulation will be delivered in a brief ramp-like manner for 30 seconds at the beginning and end of the stimulation period. The "lower" dosage condition is effectively a "sham" procedure. This approach is widely used in the field of direct current stimulation, and has been reported to be indistinguishable from the "higher" dosage protocol. This is because participants quickly habituate to the sensation of active stimulation. To assess the effectiveness of our low dose/sham stimulation, participants will be asked during Aim 2 post-testing which

dosage they believe they received and how certain they are of their opinion. They will then be informed which dosage they received.

## Locomotor training

Participants will be randomized to either the combined intervention of higher dosage tsDCS with locomotor training or lower dosage tsDCS with locomotor training. Each participant will receive up to 16 sessions of training with each session including up to 40 minutes of walking. The goal is to have participants attend 4 sessions per week for 4 weeks, but the individual schedules might vary. All sessions will be led by a licensed physical therapist with experience in walking rehabilitation after ISCI. There will be two components to the locomotor training session: 1) body-weight supported treadmill locomotor training with tsDCS (LT-TM) and 2) overground walking without tsDCS (OG).

1) LT-TM (30 min): This portion of the intervention will consist of 30 minutes of locomotor training on a treadmill and will follow standard procedures for body-weight supported treadmill locomotor training that have been published by our group and others. tsDCS, as described above, will be applied during body-weight supported treadmill locomotor training. Briefly, participants will walk on a treadmill with verbal feedback and manual assistance provided by training staff. This assistance is provided as needed to help move the leg during stepping and/or to maintain stability and balance. Avoidance of falls is assured while walking on the treadmill by an overhead body weight support safety attached to a trunk/pelvis harness. Body weight support will be set low as possible in order to allow balance responses and to afford support only as needed. Performance without compensation strategies (hip hiking, leaning to one side) will be emphasized. Rest breaks will be provided as needed.

The physical therapist leading the training will monitor for both safety and intensity of training. Self-reported level of exertion, based on the Borg scale, will be recorded. A chest-worn heart rate monitor will be used to ensure sufficient training intensities by encouraging participants to maintain a training heart rate between 70-80% of their predicted maximal heart rate. Based on this, the target training heart rate will be calculated as (220 - age) \* 70. Furthermore, the duration of stepping will be tracked and step counts will be measured using an ankle-worn accelerometer. 25,74-76 This heart rate range is based on recent evidence indicating that this intensity is safe and tolerated, and is an important factor associated with gains in locomotor function.74 Locomotor training parameters, such as walking speed, level of assistance, treadmill incline, body weight support and frequency of rest breaks will be adjusted as needed to respond to the participant's exercise tolerance and to advance the training as appropriate. A record of both training parameters and participant response will be kept in the Daily Training Log (see Information Sources and Identifier attachments). All training parameters will be adjusted for participant's tolerance, comfort and safety.

 OG (10 min): After completing the training portion described above, the tsDCS will be removed and the participant will then practice walking overground for approximately 10 minutes. Assistance of trainers will be provided as needed and the participant may use assistive device or orthotics. Rest breaks may be taken at any time.

The intervention sessions will aim to include a total of 40 minutes of stepping time, which may take up to 2 hours to complete due to set up time and rest breaks.

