#### Inclusion criteria

- 1) Male or female, ages 18-65
- 2) Single spinal cord injury (duration >1 year) classified as neurologic level T12 or above based on the International Standards for the Neurologic Classification of Spinal Cord Injury, and classified on the American Spinal Cord Injury Association (ASIA) Impairment Scale (AIS) as 'C' or 'D' motor incomplete
- 3) Capable of ambulating 10 feet with or without the use of gait devices, braces, or the assistance of one person
- 4) Medically stable with no acute illness or infection
- 5) Able to provide informed consent

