# Safety monitoring

Although numerous studies indicate tsDCS is easily tolerated and no adverse responses have been reported, 15,51 we will closely monitor participant responses. At each session the participant and physical therapist will complete a questionnaire to document any side effects such as stimulation site discomfort or skin irritation. While we do not expect any issues, we will monitor the skin closely. If any changes are observed beyond mild redness or if persistent discomfort is reported, stimulation intensity will be reduced (or discontinued, if necessary) during that training session and increased to 2.5mA in subsequent sessions if tolerated. Irritation could also occur if the harness is not fitted or positioned correctly, so this will be closely monitored and adjustments will be made as needed. In accordance with University of Florida IRB policy, adverse events that are both unexpected and serious will be reported within 5 working days.

The testing and intervention procedures could be tiring for some individuals. All participants will be given rest breaks and informed that they may rest or terminate their participation at any time. Blood pressure (BP) and heart rate (HR) will be monitored during each testing and intervention session. BP and HR must be within a medically-acceptable range for the participant to participate in a testing or training session. Resting diastolic BP must be less than 100mmHg to begin the session. The criteria for termination include complaints or symptoms of confusion, dyspnea, onset of angina, excessive blood pressure changes (systolic BP greater than 200mmHg or diastolic BP greater than 110mmHg). In addition, should the participant's HR exceed 85% of the predicted maximum HR or the participant reports a Borg rating of perceived exertion (RPE) rate of greater than 17/20, then the session will be slowed and/or halted. If the session is halted,

the participant will be asked to rest while BP and HR are monitored and will resume only when BP and HR return to acceptable values and the participant reports no other symptoms. If any of these conditions persist after rest, the participant's primary physician and/or the study physician may be contacted and the participant may be referred for evaluation. If the participant complains of angina at rest, loss of consciousness occurs, or cardiac arrest, emergency medical services through 911 will be called immediately.

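### Does the heart-rate formula printed with a bare 70 in the locomotor training section leave the training intensity target wrong or undefined?

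*Combined protocol and SAP*

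**What the plan says.** Under Locomotor training in the Research Plan, the protocol describes how intensity is steered during the treadmill component. The purpose comes first: "A chest-worn heart rate monitor will be used to ensure sufficient training intensities". In the same sentence participants are encouraged to "maintain a training heart rate between 70-80% of their predicted maximal heart rate". The next sentence reads "Based on this, the target training heart rate will be calculated as (220 - age"), and the bracket is then multiplied by 70 with no percentage scale. After a sentence on stepping duration and step counts, the text justifies the intensity: "This heart rate range is based on recent evidence indicating that this intensity is safe and tolerated".

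Two other places bear on the point. The Inclusion criteria set the ages: "Male or female, ages 18-65". The Safety monitoring section has a separate threshold for slowing or halting a session: "should the participant's HR exceed 85% of the predicted maximum HR". That section does not define predicted maximum. No other part of the document repeats or corrects the formula.

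**The concern.** The formula is introduced as a consequence of the 70-80% range, and it seems to fail that description in two ways.

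- **Scale.** Multiplying predicted maximum by 70 rather than by 70% gives a number 100 times too large.
- **Range.** Even with the percentage restored, one multiplier returns one number, while the sentence before it names an interval and a later sentence again speaks of a range. The protocol calls the computed number the target, not a minimum.

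This is the only heart-rate calculation in the document. The protocol itself links training intensity to locomotor gains, and the primary outcomes of Aim 2 are walking speed and endurance. If therapists could not tell what intensity to aim for, the training given in both arms might vary from person to person and be hard to replicate.

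**Working it through.** **Inputs.** Ages 18 and 65 are the limits in the Inclusion criteria; age 40 is added as an illustration between them. Predicted maximum is taken as 220 − age, the term in the protocol's own formula. The range of 70-80% and the multiplier 70 come from Locomotor training, and the 85% threshold from Safety monitoring. Using 220 − age for the 85% threshold is an assumption.

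**Step 1: the printed formula.** (220 − 18) × 70 = 202 × 70 = 14,140. (220 − 40) × 70 = 180 × 70 = 12,600. (220 − 65) × 70 = 155 × 70 = 10,850.

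**Step 2: the 70 read as a percentage, set against the stated range and the 85% threshold (beats per minute).**

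| Age | 220 − age | × 0.70 | × 0.80 | Width of range | × 0.85 |
|---|---|---|---|---|---|
| 18 | 202 | 141.4 | 161.6 | 20.2 | 171.7 |
| 40 | 180 | 126.0 | 144.0 | 18.0 | 153.0 |
| 65 | 155 | 108.5 | 124.0 | 15.5 | 131.75 |

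Read this way, the formula reproduces the lower limit of the range exactly at every age. It does not produce the upper limit, which lies 15.5 to 20.2 beats per minute higher.

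**Step 3: does the lower limit contradict the range?** No. The 70% value belongs to the range. The monitor's stated purpose is that intensity should be sufficient, and for that purpose the lower limit is the number one would compute. The later reference to a heart rate range most naturally points back to 70-80%, the only range given there, and not to the output of the formula. The upper limit is not lost, because the preceding sentence states it.

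**Step 4: does the 85% threshold clash with either reading?** No. On the same predicted maximum it lies above the top of the range by 171.7 − 161.6 = 10.1, 153.0 − 144.0 = 9.0 and 131.75 − 124.0 = 7.75 beats per minute.

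**Step 5: does anything statistical use the number?** No. The Statistical Plan compares pre-test to post-test change between the two dosage groups through the time-by-group interaction, and heart rate is not a term in that model. The training text is the same for both groups, so a loose reading builds in no difference between them.

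**The case for a change.** The strongest case for acting is that the typing-slip explanation settles only the scale. Restoring a percent sign or decimal point still leaves a single value, which the protocol labels the target. The protocol never says that a minimum is meant, and a reader should not have to infer it. The correction would cost one line. The 85% threshold also relies on a predicted maximum whose only available definition is the bracket inside this formula.

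Part of this stands. The label is loose, and nothing on the page states that the number is a lower limit. It is also not proven that the symbol was lost in reading the PDF: the percent sign survives in the 70-80% figure in the same section, although other marks there are damaged (reference superscripts are flattened, and the overground item has lost its list number).

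What does not stand is the step from loose wording to an unusable target. The 70-80% sentence supplies both limits by itself, so the formula removes nothing from the plan. Heart rate is also not the only guide to intensity: perceived exertion, stepping duration and step counts are recorded as well, and training parameters are adjusted to each participant's tolerance. The undefined predicted maximum under Safety monitoring is a missing detail, not a contradiction.

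**Conclusion.** The observation is accurate but does not call for a change. The literal result of 10,850 to 14,140 is a notation slip that any reader will recognise. Read as a percentage, the formula gives 108.5 to 141.4 beats per minute over the eligible ages, and this agrees with the lower limit of the range stated immediately before it. The part of the range that the formula does not compute, 15.5 to 20.2 beats per minute, is already covered by that sentence. The effect on sample size, randomisation and analysis is nil.

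The conclusion rests on two assumptions: that the bare 70 stands for 70%, which is the only reading that yields a possible heart rate and fits the adjacent sentence, and that therapists work from the range given in words. It makes no judgement about which training intensity is appropriate; that is for the investigators. They may tidy the line whenever the document is next revised, but nothing in the trial's conduct or its results waits on it.
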